#### 4.2.3 Masking

The participant's treatment assignment (pitavastatin versus placebo) will be obtained from the randomization computer at the DCC by the responsible pharmacist. The pitavastatin and placebo pills will be identical in size and shape, ensuring that neither participant nor investigator will be able to determine the treatment assignment. Participants, parents, providers and investigators will be masked to study assignment during the trial. Only designated DCC staff and site research pharmacists will be aware of treatment assignment. Given the relatively low side-effect profile of pitavastatin, it is unlikely, although not impossible, that patients will be able to guess their treatment assignment. All study measures will be obtained without knowledge of the participant's treatment assignment.

Because of the anticipated difference in lipid results between the two groups, knowledge of the full results of fasting lipid profiles would result in unmasking. However, knowledge of TG and HDL-C results are useful in informing lifestyle counseling, and extremely elevated TGs are a safety measure. Knowledge of these results would not be anticipated to result in unmasking, as these values have not been significantly impacted by statins in pediatric trials. For these reasons and for quality control purposes, fasting lipid profiles will be assessed in a centralized core lab, and results of TG and HDL-C only will be shared with the study center team and participants. LDL-C levels will be monitored by the core lab, and if the value is ≥160 mg/dL for more than six months on two successive measures, the DCC and site PI will be informed. This is anticipated to be a rare event, although it may result in a decision to discontinue study drug and start statin therapy based on clinical recommendations (see **Section 6.2.2**). The participant will continue to be enrolled in the trial and have all study measures, as per intention to treat.

Likewise, results from NMR lipoprotein fractions performed in the core lab will not be shared with study sites until all participants at all sites have completed the trial.

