# **Lipid Measures**

**Standard Fasting Lipid Profile (FLP):** A standard FLP measures total cholesterol, TG, and HDL-C, from which non-HDL-C can be calculated and LDL-C can be accurately calculated provided TG levels are <400 mg/dL. FLP remains the cornerstone for assessment of cardiovascular risk and guidance of primary prevention therapies. FLP will be obtained at all study visits and measured in the core lab. Total cholesterol and LDL-C results will not be made available to clinicians as the results could lead to unmasking.

Methods: Total cholesterol, TG and HDL-C will be measured at a centralized core laboratory using enzymatic assay, with calculation of LDL-C via the Friedwald equation, and direct LDL-C measurement if the TG level exceeds 400 mg/dL. LDL-C (direct) is measured by a homogeneous enzymatic assay.

*NMR Spectroscopy Lipoprotein Particle Assessment:* Lipids are carried within lipoprotein particles that are heterogeneous in size, density, charge, core lipid composition, specific apolipoproteins and function. Knowledge of the full lipid phenotype will inform the understanding of the CVD risk associated with CDO. Beyond the alteration of lipoprotein metabolism visible on the standard lipid profile (TG and non-HDL-C elevation and HDL-C reduction), extensive interrelated changes in lipoprotein subclass levels and particle size distributions are predictive of cardiometabolic risk. NMR spectroscopy assessment will be performed at baseline, and 6, 12 and 24 months after randomization.

Methods: The lipoprotein particle concentrations and size will be batched and measured on frozen plasma specimens (-70°C) by proton NMR spectroscopy at a centralized core laboratory. Particle concentrations of lipoprotein subclasses of different sizes will be directly obtained from the measured amplitudes of their spectroscopically distinct lipid methyl group NMR signals. Signals, and HDL particle subclasses of varying size will be quantified from the amplitudes of their spectroscopically-distinct lipid methyl group NMR signals. VLDL-P, LDL-P, and HDL-P are the totals of the particle number concentrations of their respective subclasses and their weighted-average particle sizes will be calculated from the sum of the diameter of each subclass multiplied by its relative mass percentage estimated from the amplitude of its methyl NMR signal. Signal Signal

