
#### 4.3.4 Schedule of Measurements

Table 1. Schedule of Visits/Measurements (months from randomization)

Measurement			Time	point/N	1onth		
Timepoint/Month	SV^	0	1	6	12	18	24
Vascular measures (PWV, CIMT, carotid stiffness)		Х		Х	Х		Х
Fasting lipid profile^^	Х	Χ	Χ	Χ	Χ	Χ	Χ
Lipid NMR spectroscopy, apolipoproteins		Χ		Χ	Χ		Χ
Metabolic panel, urinalysis, TSH, fasting glucose, HbA1c*, CBC**	Х						
Urine pregnancy test ¥	Х	Χ					
AST, ALT	Х	Χ	Χ	Х	X	X	Χ
Glucose homeostasis - fasting glucose, HbA1c		Χ	Х	X	X	X	X
Glucose homeostasis – insulin, C-peptide		X		Χ	X	X	Χ
CK, muscle symptoms	Х	X	Χ	X	X	X	Χ
Clinical and family history, pregnancy/contraception counseling	Х	X	X	Х	X	Х	Х
Anthropometry, blood pressure	X	X		Х	Χ	Χ	Χ
Lifestyle assessment		X		Χ	Χ		Χ
Socioeconomic status		X					
Tanner staging (self report)		X		Χ	Χ		Χ
Adverse event assessment		X	Χ	Χ	Χ	Χ	Χ
hs-CRP		Χ		Χ	Χ		Χ
DNA banking (+CBC at 24 months only)		Χ					Χ
Plasma/serum banking		Χ		Χ	Χ	Χ	Χ
Urine banking		Χ		Χ			Χ
Estimated amount of blood draw (mL)	7	37	11	34	34	31	37
Estimated visit duration (hours)	1-2	2-4	1-2	2-4	2-4	1-2	2-4

^ SV = screening visit (interval between SV and randomization minimum 2 weeks; maximum 6 weeks); Study visit windows for month 1 visit is ±2 weeks, month 6 to 18 are ±4 weeks, and month 24 is ±6 weeks.

- \* HbA1c must be done at a site lab and not point of care.
- \*\* CBC differential must include absolute counts of both segmented and band neutrophils.
- \* After screening and baseline, urine pregnancy tests may be performed at subsequent times at the discretion of site study personnel.

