# Indications for permanent discontinuation of study drug:

- Participant (or legal guardian) declines further medication participation but wishes to remain in the study.
- For elevations of ALT and other liver abnormalities, please see the table under Section
   5.3.1 for specific guidance regarding permanent discontinuation.
- Diagnosis of new liver disease other than NAFLD.
- CK elevation or symptoms without documented clinical explanation that return within 4
  weeks of restarting study drug after temporary discontinuation.
- CK elevation or symptoms that persist for more than 4 weeks after temporary discontinuation of study drug.
- New onset diabetes, at the discretion of the treating endocrinologist.
- Participants who develop LDL-C ≥160 mg/dL during the trial continuously for at least 6 months will have permanent discontinuation of study drug, will be treated with a statin (preference will be pitavastatin 4 mg per day) at the discretion of the treating physician and will continue full participation in the trial.
- Participants who develop TG ≥500 mg/dL during the trial on at least 2 consecutive assessments will continue study drug and continue full participation in the trial, and may be treated at the discretion of their health care provider. If lipid-lowering medication is started, study drug will be permanently discontinued and the participant will continue full participation in the trial.
- Pregnancy or planning pregnancy.

\*\* Symptoms will include appearance of fatigue, nausea, vomiting, right upper quadrant pain or tenderness, fever, rash, and/or eosinophilia [>5%] in combination with elevations in liver enzymes.

- Participant has bariatric surgery during the course of the study.
- Other adverse events that are thought to be related to the study drug, in the judgment of the study investigator in consultation with the DCC, PHN Medical Monitor and DSMB.
- If a participant requires prolonged use >4 weeks of a prohibited medication (protease inhibitor, warfarin, colchicine, erythromycin, rifampin, cyclosporine).

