# **6.2.2 Restrictions Regarding Concomitant Treatment**

All medication, nutriceutical and concomitant treatments will be tracked at study entry and throughout the trial. Prohibited or discouraged concomitant treatments during the trial include:

- Lipid-lowering medications are prohibited at study entry and throughout the trial. Participants who develop LDL-C ≥160 mg/dL during the trial continuously for at least 6 months will have permanent discontinuation of study drug, will be treated preferably with a statin at the discretion of the treating physician (preference will be pitavastatin 4 mg per day if available, otherwise an available statin and dose of the treating provider's choice) and will continue full participation in the trial. Participants who develop TG ≥500 mg/dL during the trial on at least 2 consecutive assessments will continue study drug and continue full participation in the trial, and may be treated at the discretion of their health care provider. If lipid-lowering medication is started, study drug will be permanently discontinued and the participant will continue full participation in the trial.
- Anti-hypertensive medications are prohibited at study entry, but are permitted for treatment as per AAP guidelines should the participant develop hypertension during the trial. The preferred medication for treatment will be lisinopril as a first line agent, and hydrochlorothiazide as a second line agent. Participants who begin taking antihypertensive medication will continue full participation in the trial, including study drug.

- Insulin and insulin-sensitizing agents are prohibited at study entry, but are permitted at
  the discretion of the treating physician for treatment as per American Diabetes
  Association (ADA) guidelines should the participant develop incident diabetes.
  Participants who begin taking insulin or insulin-sensitizing agents for diabetes or prediabetes/PCOS will continue full participation in the trial, including study drug.
- Use of vitamin supplementation (other than a daily multi-vitamin), products supplemented with plant stanols/sterols, and fish oil supplements is discouraged. Use of vitamin D supplements will be discouraged overall, but recorded at each study visit.

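### The LDL-C alert in Section 4.2.3 and the stopping rule in Sections 5.3.1 and 6.2.2 differ on duration, evidence and force, and masked sites depend on the alert to apply the rule

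*Protocol*

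**What the plan says.** Section 4.2.3 (Masking) keeps LDL-C from sites and gives the core lab one exception: "if the value is ≥160 mg/dL for more than six months on two successive measures, the DCC and site PI will be informed". The consequence is worded permissively: "it may result in a decision to discontinue study drug and start statin therapy based on clinical recommendations". The sentence cross-refers to Section 6.2.2.

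Section 5.3.1, under the indications for permanent discontinuation, reads: "Participants who develop LDL-C ≥160 mg/dL during the trial continuously for at least 6 months will have permanent discontinuation of study drug". Section 6.2.2 uses the same duration and the same mandatory wording for stopping study drug. On the replacement treatment, Section 6.2.2 says that such participants "will be treated preferably with a statin at the discretion of the treating physician".

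Section 4.3.2 (Lipid Measures) states that "FLP will be obtained at all study visits and measured in the core lab", and that clinicians will not receive total cholesterol or LDL-C. Section 4.2.3 confirms that sites and participants are given only TG and HDL-C. Under Table 1 (Section 4.3.4), lipid profiles after randomization fall at months 1, 6, 12, 18 and 24. The windows are: "Study visit windows for month 1 visit is ±2 weeks, month 6 to 18 are ±4 weeks, and month 24 is ±6 weeks".

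**The concern.** One decision, taking a participant off study drug for sustained high LDL-C, is described in two ways. Because the notice in Section 4.2.3 refers to Section 6.2.2, the sections appear to state one rule, yet they do not match.

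Masking makes this more than untidy drafting. A site that cannot see LDL-C cannot apply Section 5.3.1 unaided and has to wait for the core lab. If the alert is programmed from Section 4.2.3, a participant aged 10 to 18 can satisfy a mandatory stopping rule while the site has no means of knowing it. Two sites, or the core lab and a site, could also treat identical results differently. The timing of the decision further sets when open-label statin may begin, and so enters the time-under-statin analysis planned in Section 8.1.

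**Working it through.** The protocol states no figure for this rule, so there is none to reproduce. The check is a comparison of the texts, followed by the visit arithmetic.

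**Texts side by side**

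| Element | Section 4.2.3 | Sections 5.3.1 and 6.2.2 |
|---|---|---|
| Threshold | ≥160 mg/dL | ≥160 mg/dL |
| Duration | more than 6 months | at least 6 months |
| Evidence | two successive measures | *continuously*; no number of measures given |
| Stopping study drug | may follow | will follow |
| Starting a statin | may follow | at the treating physician's discretion |

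The threshold agrees. Duration, evidence and the force of stopping do not. Starting a statin involves discretion in both, so the may/will conflict concerns stopping study drug only.

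**If nominal visit months are counted.** The gaps are 6 − 1 = 5 months, then 12 − 6 = 18 − 12 = 24 − 18 = 6 months. From month 6 onward the spacing is exactly the boundary value. For LDL-C that stays high from its first high value:

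| First high | At least 6 months met at | More than 6 months met at |
|---|---|---|
| Month 1 | 12 (11 months) | 12 (11 months) |
| Month 6 | 12 | 18 |
| Month 12 | 18 | 24 |
| Month 18 | 24 | not within the trial |

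The wordings separate by one visit for a first elevation at month 6 or 12. From month 1 there is no difference. From month 18 the difference has little practical effect, because treatment ends at month 24. A high value at month 0 is left aside: the rule concerns values that develop during the trial, and the text does not say whether baseline counts.

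**If exact dates are counted.** Each gap can move by the sum of the two adjacent windows (1 month = 365.25/12 = 30.44 days):

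- Months 1 to 6: 5 months ± (14 + 28) days, or 3.6 to 6.4 months.
- Months 6 to 12 and 12 to 18: 6 months ± (28 + 28) days, or 4.2 to 7.8 months.
- Months 18 to 24: 6 months ± (28 + 42) days, or 3.7 to 8.3 months.

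On dates, the two durations differ only when the span is exactly six months. Assume that each visit day is independent and uniform over its window (57 days for ±4 weeks, 85 days for ±6 weeks). The protocol does not state this.

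- Months 6 to 12 or 12 to 18: P(exactly six months) = 1/57 = 1.8%. By symmetry, P(more than six) = (1 − 1/57)/2 = 49.1%, and P(at least six) = 49.1% + 1.8% = 50.9%.
- Months 18 to 24: P(exactly six months) = 1/85 = 1.2%.

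So the duration wording decides the outcome for about 1 to 2% of six-month pairs when dates are used, and for every such pair when nominal months are used. The protocol does not say which count applies.

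**The case against.** The best defence is that the operative rule is consistent. Sections 5.3.1 and 6.2.2 agree with each other, while Section 4.2.3 describes a notification under a masking heading and sends the reader to Section 6.2.2 for the decision. On that view *may* is descriptive, and it covers two acts, of which one (the statin) is discretionary anyway. This has force on the may/will difference. It does not dispose of the duration, because the notification itself is tied to the longer period and the site depends on it.

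It is also fair that the durations almost never diverge on exact dates, as the working shows.

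Three stronger readings are tempting, and the protocol does not support them:

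- *Up to about 5% of participants are affected.* The feasibility audit in Section 8.2 found 22 of 454 (4.8%) with at least one LDL-C above 160 mg/dL, but describes these elevations as not continuous. It does not measure sustained elevation, and the protocol gives no rate for that.
- *The visit windows create the conflict.* About half of six-month pairs fall short of six months under either wording. That dependence belongs to any elapsed-time rule and is not evidence of contradiction.
- *The rule is the sole route to open-label treatment, so the conflict threatens the trial's power.* Sections 5.3.1 and 6.2.2 also describe a route to lipid-lowering medication through high TG. Participants who stop study drug stay in follow-up and in their randomized group, and the sample-size assumptions in Section 8.2 state that crossover was not built in.

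**Conclusion.** The point holds as a minor internal inconsistency. Section 4.2.3 conflicts with Sections 5.3.1 and 6.2.2 on duration, on the evidence required and on whether stopping study drug is mandatory. Since the alert is the only described route by which masked sites could apply the rule, a participant can meet the mandatory criterion without the site being told.

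The size depends on how six months is counted. With nominal visit months, the alert comes one visit (6 months) late relative to Sections 5.3.1 and 6.2.2 for first elevations at month 6 or 12. With exact dates, the durations differ for about 1 to 2% of pairs under the uniform-date assumption, leaving mainly the differences in evidence and force. The number of participants concerned cannot be derived from the protocol. Section 4.2.3 itself expects the event to be rare, so the effect on the primary PWV comparison is likely small. The reason to act is consistent handling of a treatment-stopping rule in minors.

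**What to change.** Reconcile Sections 4.2.3, 5.3.1 and 6.2.2 so that the alert trigger and the discontinuation rule state the same duration, the same evidence requirement and the same force for stopping study drug. Bring the core-lab alert specification into line with the agreed text. Which duration, evidence and force apply is for the sponsor to decide; this review does not favour either version. The cost is a wording amendment to the protocol and a check, or update, of the core-lab alert. Sample size, visits and analyses are unaffected.

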#### 4.2.4 Missing Data

In addition to the design features discussed above, careful treatment of missing data as described in **Section 8.5**, below, will help to detect and minimize any possible bias in reporting outcomes of this trial.

### 4.3 Study Measures

Vascular	PWV, CIMT, carotid artery stiffness
Safety	ALT, AST; fasting glucose, HbA1c, insulin, C-peptide;
	muscle symptoms, CK; adverse events
Lipids	FLP; LP subfractions (NMR); apolipoproteins
Clinical and family	Height, weight, waist circumference; BP; Tanner
Hx & P/Exam	staging; socioeconomic status; lifestyle assessment
Lab covariates	hs-CRP, banked specimens (DNA, plasma/serum)

# 4.3.1 Measures of Primary Outcome

### Vascular Measures: Pulse Wave Velocity (PWV)

PWV is a functional measure of arterial stiffness associated with atherosclerosis. It is a measure of the time taken by the pressure wave through an artery over a specific distance. PWV is measured from the carotid to femoral arteries and is a reflection of central arterial stiffness along the thoracic and abdominal aorta. Given variation in measurement technique and conditions, normal values do not currently exist.

Method: PWV will be measured with a SphygmoCor device (Atcor Medical, Sydney, Australia). With the patient supine, ECG leads are applied, and the average of 3 measurements of the distance between the two recording sites is obtained (from the carotid pulse above the sternal notch to the femoral artery pulse) and entered into the software. A high-fidelity tonometer (pressure sensor) will be placed on the carotid artery to obtain the 'proximal' pressure waveform and then on the femoral pulse to obtain the 'distal' waveform. The device will calculate PWV as the difference in the carotid-to-distal path length divided by the difference in R-wave-to-waveform times (Δdistance/Δtime, m/sec). PWV will be measured at baseline, and at 6, 12 and 24 months after randomization.

Training: Personnel (technicians, research assistants or nurses) from all sites will attend a PWV training webinar conducted by the vascular core lab. Following this, each observer will perform replicate PWV studies on volunteers; these studies will be transmitted to the core lab for analysis where reproducibility will be calculated. Observers will be 'certified' if their coefficient of variation for within- and between-visit PWV is < 10%, the threshold deemed acceptable in published guidelines. Sites will be instructed to send 1 practice study every 6 months for review and web-based re-training will be conducted prior to year 2 data collection.

Quality Control (QC): PWV is a very reproducible measure,  demonstrating a within-visit coefficient of variation of 6.2% and between-visit coefficient of variation of 5.2% in a recent analyses of adolescents (n>800 of which 2/3 were obese). Every 6 months, reproducibility for within-visit (QC) PWV reproducibility will be calculated as the coefficient of variation among the 3 replicate readings obtained during the visit by the DCC. Re-training via video-conferencing or at in-person Pediatric Heart Network (PHN) Steering Committee meetings will be provided as needed.

#### Carotid Artery Intima-Media Thickness (CIMT) and Carotid Artery Stiffness

CIMT is a structural measure of arterial wall thickness (tunica intima and tunica media – the two innermost layers of the arterial wall). It is a measure of the potential presence of atherosclerotic disease in the arterial wall. Carotid artery stiffness is another measure of vascular function that is easily obtained at the time of CIMT assessment. Given variation in measurement technique and conditions, normal values do not currently exist.

Methods: B-mode ultrasound with a high resolution linear array vascular transducer will be used to record common, bulb and internal CIMT. A Meyer's arc will record the angle at which the greatest CIMT is obtained so follow-up imaging can be obtained at the same site. Images will be stored electronically and sent to the core lab for reading. Automatic edge detection software will be used with 3 readings averaged for analysis. For carotid artery stiffness, an optimal 2-dimensional image of the common carotid artery will be obtained, and the M-mode cursor will be placed 1 cm proximal to beginning of the carotid bulb. The maximal and minimal lumen diameters will be read from the M-mode tracing for calculations of carotid artery stiffness. Calculations of carotid artery stiffness will include incremental elastic modulus (Einc), Peterson mean pressure-strain elastic modulus (PEM),Young's elastic modulus (YEM), and beta arterial stiffness index (Beta).

Training: CIMT and carotid artery stiffness assessment will be performed at each site by a trained ultrasonographer according to published pediatric guidelines. Detailed training will be provided by webinar conducted by the vascular core lab. To insure standardization, each site will send up to 5 de-identified CIMT and carotid dimension images for review prior to study initiation, at regular intervals throughout the study, and whenever there are site personnel changes. Images acceptable for reading at all 3 sites (common, bulb, internal carotid) on both sides will be required for certification.

Quality Control: A core lab study (personal communication; [name]) involving more than 800 participants showed that the coefficient of variation ranged from 1.8 (peak systolic dimension) to 5.5% (internal carotid) for within visit measures, which is acceptable according to published standards. Feeting 6 months, reproducibility for the 3 readings of the carotid ultrasound for both (QC) CIMT and stiffness will be calculated by the DCC. Re-training for each technician via video-conferencing or at in-person PHN steering committee meetings will be provided as needed. Sites will be instructed to send 1 practice study per technician every 6 months for review and webinars will be conducted prior to year 2 data collection.

